10. STATISTICAL CONSIDERATIONS

HYPOTHESIS AND ENDPOINTS

With median progression-free survival (PFS) as the primary endpoint, the primary objective of this single arm, open-label, phase II study is to determine the median PFS for FOLFIRI and panitumumab in patients with metastatic RAS wild-type colorectal carcinoma who have previously failed FOLFIRI and bevacizumab.

The secondary endpoints of this study are the frequency and severity of toxicities of the regimens, overall response rate, and overall survival rate at 1 year.

10.1. Study design and Sample Size Calculation:

The PRIME study is a phase III clinical trial, in which patients with metastatic colorectal cancer and KRAS (codon 12 and 13) wild-type tumors were randomized to FOLFOX or FOLFOX and panitumumab for first-line therapy. Retrospective analysis of the additional RAS mutations showed that patients with tumors that were RAS wild-type had a 2.2 month improvement in PFS when panitumumab was added to FOLFOX (7.9 vs. 10.1 months [HR 0.72m 95% CI 0.58-0.90, p=0.004]) (43). Patients receiving FOLFIRI plus panitumumab after failing first-line non-irinotecan containing treatment for RAS wild-type metastatic colorectal cancer patients had a reported mPFS of 5.9 months compared to 3.9 months for those treated with FOLFIRI alone (36). Also, per the BOND study, patients who had disease progression on prior irinotecan-based chemoregimens were randomized to either cetuximab monotherapy or cetuximab and irinotecan. Median time to progression was improved by 2.6 months with the combination arm (1.5 vs 4.1 months, comparing cetuximab vs cetuximab and irinotecan) (34). We expect a similar treatment effect for panitumumab and FOLFIRI in our study following FOLFIRI plus bevacizumab failure. As such, we expect our group of patients to have an improved mPFS (6 months) compared to the historical control of a similar patient population treated with irinotecan and cetuximab (3.98 months) in RAS wild-type metastatic colorectal cancer (36).

We anticipate a uniform accrual rate of 2 patients per month, no lost to follow-up, and an additional 6 months of planned follow-up after accrual is completed. A total of 25 subjects will be required to detect the difference between a median PFS of 6 months for our testing treatment and a median PFS of 4 months for the historical control assuming exponential PFS distribution. The one-sided type I error and the power have been set at 0.10 and 80% respectively when calculating the sample size using the online sample size calculator provided by SWOG (<http://www.swogstat.org/statoolsout.html>).

With a total of 25 patients, we will be able to construct 95% confidence intervals no wider than 20% for proportions. If a specific adverse event occurs with a true probability of 10%, the probability of observing one or more patients with the AE in 25 patients will be about 93%.

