3. STUDY DESIGN

3.1. Study design

This is an open-label, prospective phase II clinical trial, with a primary endpoint of progression-free survival (PFS). Patients must fail a combination of FOLFIRI and bevacizumab prior to being considered for this study. At the time of consideration, all participants will be screened for RAS mutations and only patients who are considered RAS-wild type [KRAS exon 2 (codon 12 and 13), KRAS exon 3 (codon 61) and exon 4 (codons 117 and 146) and NRAS exon 2 (codons 12 and 13), exon 3 (codon 61), and exon 4 (codons 117 and 146)] will be enrolled on the study. Patients eligible for this study will receive a modified regimen of FOLFIRI as outlined in this study along with panitumumab as outlined in section 6.2. Each cycle will consist of days 1 and 15 as outlined in section 6.2. Patients will be restaged after 2 cycles of therapy. If there is no evidence of progressive disease, patient will continue on study. They will be monitored at regular intervals with serial laboratory testing as well as periodic scans to assess response to treatment as outlined in section 5.5.

3.2 Sample Size and Accrual Rate:

A total of 25 patients will be required to test the null hypothesis that there is no difference in median PFS between the study regimen and the historical control. Please refer to Section 9 for details regarding the statistical methods. We anticipate a uniform accrual rate of 2 patients with KRAS wild type mCRC per month from the 2 participating institutions (The Ohio State University (lead)), no lost to follow-up, and an additional 6 months of planned follow-up after accrual is completed.

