10.2. Analysis of Primary and Secondary Efficacy Parameters

Continuous variables will be expressed by means, standard deviations and 95% confidence intervals. Frequencies will be computed for discrete data. Median PFS will be estimated using the Kaplan-Meier estimator with confidence interval calculated based on the Brookmeyer-Crowley method (38). Kaplan-Meier estimator will be used also to estimate OS rate at 1 year.

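### Section 10.1 claims 80% power, but 25 patients at the stated accrual and follow-up give about 68–71% for a median PFS of 6 versus 4 months

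*Combined protocol and SAP*

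**What the plan says.** The sizing is in Section 10.1: "A total of 25 subjects will be required to detect the difference between a median PFS of 6 months for our testing treatment", compared with 4 months for the historical control, with PFS assumed exponential. The error rates follow: "The one-sided type I error and the power have been set at 0.10 and 80% respectively when calculating the sample size". The source is an online SWOG calculator. The routine, the test statistic and the number of events are not given.

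Section 3.2 repeats the sample size in the language of a test: "A total of 25 patients will be required to test the null hypothesis that there is no difference in median PFS". It also repeats the timing: uniform accrual of 2 patients per month, "no lost to follow-up, and an additional 6 months of planned follow-up after accrual is completed".

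The analysis text describes estimation only. Section 10 opens by saying that "the primary objective of this single arm, open-label, phase II study is to determine the median PFS", and Section 10.2 says: "Median PFS will be estimated using the Kaplan-Meier estimator with confidence interval calculated based on the Brookmeyer-Crowley method". It gives no test, critical value or decision rule.

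**The concern.** A quick count raises the doubt. On the usual log-hazard scale, detecting a median ratio of 6/4 = 1.5 in a single arm, at one-sided 0.10 with 80% power, takes

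(1.2816 + 0.8416)² / (ln 1.5)² = 27.4 events.

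That is more events than there are patients, and with only 6 months of follow-up after accrual some patients will still be progression-free at the cut.

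The power is the main operating characteristic stated for the primary endpoint. If it is overstated, a result that fails to exclude 4 months will be read as stronger evidence against the regimen than it is.

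**Working it through.** **Inputs (all from Sections 10.1 and 3.2).** N = 25; null median 4 months; alternative median 6 months; exponential PFS; one-sided 0.10 (z = 1.2816); 80% power (z = 0.8416); 2 patients per month, so accrual a = 25/2 = 12.5 months; follow-up f = 6 months; no loss to follow-up.

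**Expected events.** P(event) = 1 − [exp(−λf) − exp(−λ(a+f))] / (λa), with λ = ln 2 / median.

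- Median 6: 1 − (0.5000 − 0.1180)/1.4441 = 0.7355, giving 18.4 events.
- Median 4: 1 − (0.3536 − 0.0405)/2.1661 = 0.8555, giving 21.4 events.

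**A route to 25.** A linear-scale shortcut lands on the plan's number. Events = (1.2816 + 0.8416)² / (1.5 − 1)² = 18.03, and 18.03/0.7355 = 24.5 patients. Nominal power is Φ(√18.39 × 0.5 − 1.2816) = 80.6%. That this is what the calculator did is an inference, because the routine is not named.

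The shortcut uses the null standard error of the estimated median ratio, 1/√d, under the alternative as well. At a true ratio of 1.5 the standard error is 1.5/√d, and the power becomes Φ[(√18.39 × 0.5 − 1.2816)/1.5] = 71.7%. A simulated test of this form had size 11.4% and power 73.6%, so it misses 80% even while exceeding the stated alpha.

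**Power at N = 25.** On the log-hazard scale, Φ(√18.39 × ln 1.5 − 1.2816) = 67.6%. Simulation (600,000 trials per hypothesis, uniform entry over 12.5 months) gives:

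| Test against 4 months, one-sided 0.10 | Attained size | Power at 6 months |
|---|---|---|
| One-sample log-rank, nominal cut-off | 8.5% | 68.0% |
| Exponential estimate, calibrated | 10% | 70.9% |
| Neyman-Pearson likelihood ratio, calibrated | 10% | 71.0% |

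The last row is the ceiling. Between two fully specified exponential distributions, no test of the same size is more powerful. Using the unrounded control median of 3.98 months from Section 10.1 moves the range only to about 69–71%. If all 25 patients were followed to an event, power would still be only about 78%.

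**What 80% would take at the stated alpha.**

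| Route | Exponential test | One-sample log-rank |
|---|---|---|
| True median detectable, N = 25 | about 6.4–6.5 months | about 6.6 months |
| N at 2 per month, 6 months of follow-up | 33 (80.5%) | 35 (80.3%) |

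A later PFS cut with 25 patients does not reach 80%. At 12 or 18 months after last entry, the exponential test has 75.4% or 76.6% and the log-rank 72.3% or 73.8%.

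**If the Section 10.2 interval decided the trial.** Every patient has at least 6 months of follow-up, so the number progression-free at 4 months is binomial with probability 0.5 under the null and 2^(−4/6) = 0.630 under the alternative. The lower limit exceeds 4 months in these cases:

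- One-sided 90% limit: at least 16 of 25; size 11.5%, power 54.8% (about 51% if held to exactly 10%).
- Two-sided 95% interval: at least 18 of 25; size 2.2%, power 23.7%.

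**The case against.** Several points can be made for the plan.

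- **The objective is estimation.** The plan sets out to determine a median and will report one with an interval. A miss rate of 29–32% therefore belongs to a test that the plan does not contain. This is fair as far as it goes, and the figure should be read as conditional on a one-sample test. But Sections 3.2 and 10.1 justify the 25 patients by a hypothesis test with stated error rates, and that justification is what fails.
- **The calculator may have returned 25.** It may have done so, and its routine cannot be identified. The result does not depend on the answer, because the ceiling applies to any valid test.
- **The timing is a planning assumption.** Patients are treated and scanned until progression, so a later cut or slower accrual would add events. This is true: at 1 patient per month the ceiling is about 74%, and with complete follow-up about 78%. The gap narrows but does not close.
- **The interval-based figures are fragile.** They rest on a decision rule that the plan does not state and on continuously observed progression, whereas scans are every 8 weeks. If progression were recorded only at scans, the same cut-offs would give about 64.5% power with size 18.0% (at least 16 of 25) and 32% with size 4.1% (at least 18). This stands: those figures are illustrative only.
- **The trial is small and already accruing.** The reported median and interval do not change with the power. That limits the remedy to wording but does not make the stated power correct.

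**Conclusion.** The stated 80% is wrong as written. With the plan's own inputs, power is about 68% for a one-sample log-rank test and 71% at most for any valid test at one-sided 0.10, a shortfall of 9–12 percentage points. This assumes exponential PFS, uniform accrual over 12.5 months, a cut 6 months after last entry and no losses, all of which the plan states. The one element supplied here is the test itself, because Section 10.2 names none. Where the number 25 came from remains unknown.

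**What to change.** In Section 10.1, name the test and replace the power statement, for example:

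> With 25 patients, 12.5 months of accrual and 6 months of further follow-up, about 18 PFS events are expected if the true median is 6 months. A one-sample log-rank test against a 4-month exponential median at one-sided 0.10 has about 68% power, and reaches 80% at a true median of about 6.6 months.

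If a calibrated exponential test is chosen, the figures are about 71% and about 6.5 months. Make Section 3.2 agree. Add the chosen test to Section 10.2, so that the power belongs to an analysis that will be run, and state that this power does not apply to a decision based on the Brookmeyer-Crowley interval. The cost is wording and a less favourable stated power.

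Optional changes:

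- Take the primary PFS cut 12–18 months after last entry and state the resulting power (about 75–77% exponential, 72–74% log-rank). This delays the readout by 6–12 months and adds no patients.
- Keep 80% at the stated timing with 33–35 patients. This adds 8–10 patients, or 4–5 months of accrual at 2 per month.

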2.2 Secondary Objectives

- To determine the frequency and severity of toxicities of the regimens.
- To determine overall response rate
- To determine the median overall survival and the overall survival rate at 1 year

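### With 25 patients, 95% confidence intervals for proportions are up to 39 to 41 percentage points wide, about twice the 20% stated in Section 10.1

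*Combined protocol and SAP*

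**What the plan says.** After setting the sample size from the PFS comparison, Section 10.1 adds a statement on precision: "With a total of 25 patients, we will be able to construct 95% confidence intervals no wider than 20% for proportions". It gives no formula, no interval method and no assumed proportion, and it does not describe the 20% as a half-width, a margin of error or a plus-or-minus figure.

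The proportions it can apply to are among the endpoints listed at the start of Section 10: "The secondary endpoints of this study are the frequency and severity of toxicities of the regimens, overall response rate, and overall survival rate at 1" (the last item being the one-year rate). Section 2.2 also lists response among the objectives: "To determine overall response rate".

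Section 10.2 does not add to this. It names an interval method for median PFS (Brookmeyer-Crowley). For categorical data it says only: "Frequencies will be computed for discrete data".

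**The concern.** The width of a confidence interval is its upper limit minus its lower limit. An upper bound on that width, given without conditions, is a guarantee for every proportion the trial might observe. At n = 25 the standard error of a proportion near one half is 10 points, so a 95% interval must span roughly 39 points. A 20-point ceiling looks like the half-width reported as the whole.

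At stake is what a reader expects the trial to show about response and toxicity. Taken literally, the sentence suggests that an observed response rate of 20% would be pinned down to something like 10% to 30%. The trial cannot do that, and no other statement in the plan tells the reader how precise these rates will be.

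**Working it through.** **Inputs**

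- n = 25, single arm (Section 10.1: "A total of 25 subjects will be required to detect the difference between a median PFS of 6 months for our testing treatment").
- Confidence level 95%, taken as two-sided.
- No reduction of n, because Section 10.1 assumes "no lost to follow-up, and an additional 6 months of planned follow-up after accrual is completed".
- Assumed proportion: not given. A bound of the form "confidence intervals no wider than 20% for proportions" implies the worst case, p = 0.5 (my assumption).
- Interval method: not given, so several were tried.

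**Step 1. Where the 20% comes from**

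Normal approximation, half-width at p = 0.5:

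1.96 × √(p(1 − p)/n) = 1.96 × √(0.25/25) = 1.96 × 0.10 = 0.196, or 19.6 points.

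Of the variants tried, this normal-approximation half-width is the one that accounts for the stated figure.

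**Step 2. The width**

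Full width at p = 0.5: 2 × 0.196 = 0.392, or 39.2 points, which is 39.2/20 = 1.96 times the stated limit.

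The exact method takes the lower limit as the 2.5% quantile of Beta(x, n − x + 1) and the upper limit as the 97.5% quantile of Beta(x + 1, n − x). Its widest interval is at 12 of 25: 27.8% to 68.7%, 40.9 points.

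Maximum full width over all possible counts with n = 25:

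| Method | Maximum width (points) |
|---|---|
| Normal approximation | 39.2 |
| Clopper-Pearson (exact) | 40.9 |
| Jeffreys | 37.4 |
| Wilson | 36.5 |
| Agresti-Coull | 36.5 |

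None comes near 20. A lower confidence level does not help: the worst-case width by the normal approximation is 32.9 points at 90% and 25.6 points at 80%.

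**Step 3. Widths at particular counts**

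Normal-approximation limits are cut off at 0.

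| Events of 25 | Observed rate | Normal (points) | Wilson (points) | Exact (points) |
|---|---|---|---|---|
| 0 | 0% | 0.0 | 13.3 | 13.7 |
| 1 | 4% | 11.7 | 18.8 | 20.3 |
| 2 | 8% | 18.6 | 22.7 | 25.0 |
| 3 | 12% | 24.7 | 25.8 | 28.7 |
| 5 | 20% | 31.4 | 30.3 | 33.9 |
| 8 | 32% | 36.6 | 34.4 | 38.6 |
| 12 | 48% | 39.2 | 36.5 | 40.9 |

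A width of 20 points or less occurs only at the extremes: 0 to 2 or 23 to 25 events by the normal approximation with limits cut off at 0 and 1, 0 to 1 or 24 to 25 by Wilson, and 0 or 25 by the exact method. Without the cut-off, the normal-approximation width at 2 of 25 is 21.3 points, so that range shrinks to 0 to 1 or 24 to 25.

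The 20% row matters most. Section 1.3 cites response rates above 20% for irinotecan with cetuximab after irinotecan failure, and below 25% for other second-line regimens. At 5 of 25 the exact interval is 6.8% to 40.7%.

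**Step 4. What a 20-point width would take**

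Normal approximation at p = 0.5: n = (1.96/0.10)² × 0.25 = 96.04, so 97 patients. A search over n gives 93 for Wilson and 104 for the exact method.

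**Step 5. Check on the neighbouring figure**

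The next sentence in Section 10.1 begins "If a specific adverse event occurs with a true probability of 10%, the probability of observing one or more patients with the AE in 25" and puts that probability at about 93%. It reproduces: 1 − 0.9²⁵ = 0.928. So n = 25 is the right basis, and the fault lies only in the sentence on width.

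**The case against.** The strongest reply is that this is a slip of wording and not a wrong calculation. The authors evidently computed 19.6 points correctly and left out plus or minus. Read that way, the bound holds for the normal approximation (19.6) and for Wilson (18.2). The exact half-width reaches 20.4, but the excess is 0.4 points and the plan does not commit to the exact method, so little should be made of it.

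That account of the origin is very likely right, and it shows how small the repair is. It does not make the sentence true. Nothing in Section 10.1 or elsewhere signals a half-width, and a reader is entitled to take a statement about how wide an interval is at face value.

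The second reply is that little depends on the sentence. This stands. The 25 patients are justified by the PFS comparison, no decision or stopping rule uses the interval width, and the reported intervals will be computed from the data whatever the plan says. The harm is limited to the precision that the plan promises for its secondary endpoints.

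A third reply is that the choice among exact, Wilson and Jeffreys intervals is a matter of preference. This also stands: naming a method is useful, because Section 10.2 names none for proportions, but the sentence can be corrected without it.

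**Conclusion.** The statement is wrong as written. With 25 patients the maximum width of a 95% interval for a proportion is 39.2 points (normal approximation) to 40.9 points (exact), about twice the 20 stated. Every common method gives at least 36.5. At a response rate of 20% the exact width is 33.9 points, 33.9/20 = 1.7 times the stated limit.

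This rests on two-sided 95% intervals, all 25 patients being evaluable, and width having its ordinary meaning. Fewer evaluable patients would widen the intervals. The figures apply directly to response and toxicity rates. They carry over to the one-year survival rate, which is to be estimated by Kaplan-Meier, only if every patient is followed for a full year.

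The likely cause is a half-width called a width. The point should be corrected, but it does not touch the sample size or the primary analysis.

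**What to change.** Replace the sentence in Section 10.1 with, for example:

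> With 25 patients, exact 95% confidence intervals for proportions will be at most 41 percentage points wide; for an observed response rate of 20% (5 of 25) the interval is 7% to 41%.

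If the authors prefer to keep the 20-point figure, they should call it a half-width and state that it is based on the normal approximation. A plus-or-minus description suits exact intervals less well, because they are not symmetric: at 5 of 25 the limits lie about 13 points below and 21 points above the estimate.

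It would also help to name in Section 10.2 the interval to be used for response and toxicity rates. Clopper-Pearson matches the wording above. If another method is chosen, the quoted maximum should change with it (for example 36.5 points for Wilson).

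The cost is one sentence, plus one phrase if the method is named. No design element, sample size or analysis changes. The stated precision becomes less favourable, but it is what 25 patients can deliver.

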10.2. Analysis of Primary and Secondary Efficacy Parameters

Continuous variables will be expressed by means, standard deviations and 95% confidence intervals. Frequencies will be computed for discrete data. Median PFS will be estimated using the Kaplan-Meier estimator with confidence interval calculated based on the Brookmeyer-Crowley method (38). Kaplan-Meier estimator will be used also to estimate OS rate at 1 year.

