6.4. Assessment during Treatment

The following will be obtained at regular intervals during treatment:

- a. History and physical examination Day 1 of each cycle
- b. Vital signs and weight assessment will be obtained prior to day 1 and day 15, (within 2 days).
- c. Drug toxicity (Adverse Drug Events) will be assessed every two weeks (toxicities will be graded according to the NCI CTC version 4.0).
- d. Complete blood count and serum chemistries (electrolytes including magnesium, calcium, potassium, BUN, Creatinine, liver function tests) will be obtained within 48 hours prior to each treatment, days 1 and 15.
- e. CEA serum level every as a baseline and once every cycle.
- f. Imaging studies including but not limited to CT scans prior to treatment as a baseline and every 8 weeks (+/- 5 days).

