6.6. Efficacy Parameters

Patients will be assessed for tumor response according to the RECIST 1.1 criteria (43) after 8 weeks of treatment, and every 8 weeks thereafter as well at the end of the study. Tumor assessments should also be made on each patient within 2 weeks of study completion, withdrawal or discontinuation, as appropriate, even if the patient demonstrates physical evidence of progressive disease and withdraws from the study before the first scheduled tumor assessment.

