8.2. Progression Free Survival (PFS)

PFS will be measured as the time from Study Day 1 to the time the patient is first recorded as having disease progression or death, whichever comes first.

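### Section 10.1 states 80% power for 25 patients, but its own exponential inputs allow at most about 71%, and section 10.2 names no test or success rule for that comparison

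*Combined protocol and SAP*

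**What the plan says.** Section 3.2 presents the sample size as the basis of a test: "A total of 25 patients will be required to test the null hypothesis that there is no difference in median PFS" between the regimen and the historical control. It sends the reader to Section 9 for methods, but Section 9 is safety and the statistics are in Section 10.

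Section 10.1 gives the design inputs:

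- 4 months for the control against 6 months for the regimen, with exponential PFS.
- Error rates: "The one-sided type I error and the power have been set at 0.10 and 80% respectively".
- Accrual and follow-up: "We anticipate a uniform accrual rate of 2 patients per month, no lost to follow-up, and an additional 6 months of planned follow-up" once accrual ends.
- The calculation came from an online SWOG calculator. The module and formula are not given.
- The control is described as a "historical control of a similar patient population treated with irinotecan and cetuximab (3.98 months"), rounded to 4 for the calculation.

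Section 10.2 is the only analysis text for the primary endpoint: "Median PFS will be estimated using the Kaplan-Meier estimator with confidence interval calculated based on the Brookmeyer-Crowley method (38").

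On dating of events, section 8.2 counts PFS to "the time the patient is first recorded as having disease progression or death". Section 6.6 schedules tumour assessment "after 8 weeks of treatment, and every 8 weeks thereafter as well at the end of the study", and section 6.4 schedules "CT scans prior to treatment as a baseline and every 8 weeks (+/- 5 days").

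**The concern.** There are two gaps. First, the stated power is higher than the stated inputs can deliver, so the trial is less likely to detect its target effect than its readers are told. Second, the test that was sized is never written into the analysis. Section 10.1 fixes the null, the alternative, alpha and the model. The test statistic and the success rule stay open, and so does the handling of progression that is only seen at scans.

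The open choices matter because plausible rules differ in power and in type I error. A rule chosen after the data are seen could change whether the result is called positive.

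**Working it through.** **Inputs (section 10.1).** N = 25; medians 4 and 6 months, exponential, so λ0 = ln 2/4 = 0.1733 and λ1 = ln 2/6 = 0.1155 per month; accrual A = 25/2 = 12.5 months; further follow-up F = 6 months; no loss; one-sided alpha 0.10 (z = 1.2816).

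**Step 1. Expected events.** P(event) = 1 − [exp(−λF) − exp(−λ(A+F))]/(λA).

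- At 6 months: 1 − (0.5000 − 0.1180)/1.444 = 0.735, giving 25 × 0.735 = 18.4 events.
- At 4 months: 1 − (0.3536 − 0.0405)/2.166 = 0.855, giving 21.4 events.

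**Step 2. Attempt to reproduce 25 patients and 80%.** On the log-hazard scale, 80% power needs (1.2816 + 0.8416)²/(ln 1.5)² = 27.4 events. With 18.4 events, power is Φ(√18.4 × ln 1.5 − 1.2816) = 0.676. Eight standard one-sample formulas were solved for 80% power with accrual at 2 per month. Seven need 31 to 36 patients. The eighth, a log-rank approximation with null variance, needs 27. At N = 25 that last formula claims 77.7%, but the test simulates at 71.8% power with actual alpha 0.104. The stated figure was not reproduced.

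**Step 3. Ceiling for any test.** With D events and total time at risk T, the most powerful test of 4 against 6 months uses D·ln(λ1/λ0) − (λ1 − λ0)·T, calibrated to alpha 0.10. Simulation of the planned design (400,000 trials) gives:

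| Test at N = 25 | Actual alpha | Power |
|---|---|---|
| Most powerful, calibrated | 0.100 | 0.71 |
| One-sample log-rank, (E − D)/√E ≥ 1.2816, E = λ0T | 0.084 | 0.68 |
| One-sided 90% profile-likelihood bound above 4 months | 0.094 | 0.70 |

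Using 3.98 instead of 4 months moves the ceiling to about 72%. The calibrated test needs about 33 patients for 80% (32 gives 79.6%).

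**Step 4. Longer follow-up.** The ceiling at N = 25 rises to about 74% with 9 months of follow-up, 75% with 12 and 77% with 18. With every patient followed to an event, power is P(χ²₅₀ > (4/6) × 63.17) = P(χ²₅₀ > 42.11) = 0.778. The same formula reaches 0.800 only at 27 events.

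**Step 5. Effect of leaving the rule open (illustration; the plan states no such rule).** Suppose success meant a Brookmeyer-Crowley lower limit above 4 months. No patient is censored before 6 months, so the Kaplan-Meier value at 4 months is X/25 with X binomial. For a two-sided 80% interval, X = 16 passes, since (0.64 − 0.50)/√(0.64 × 0.36/25) = 1.46, and X = 15 fails, at 1.02. At a 6-month median, S(4) = 2^(−4/6) = 0.630 and P(X ≥ 16) = 0.548; at a 4-month median the same probability is 0.115. At the 95% level, needing 17 or 18 of 25, power is 38% or 24%.

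**Step 6. Scan dating.** Eight weeks is 1.84 months. Apply the one-sample log-rank at 1.2816 to recorded dates, with the null at 4 months. The ranges run from censoring at the last scan to censoring at the data cutoff.

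- If 4 months is an exact-time median: alpha 0.233 to 0.291.
- If 4 and 6 months are both scan-dated on a similar schedule (assumption: mean recorded time = median/ln 2, so the underlying exact medians are 3.32 and 5.34): alpha 0.052 to 0.075, power 0.707 to 0.763.

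**The case against.** The stated objective is to determine the median, and a Kaplan-Meier estimate with a Brookmeyer-Crowley interval serves that. This would answer the missing test if estimation were the whole aim. It does not fit section 3.2, which says the 25 patients are needed to test a null hypothesis, or section 10.1, which sets alpha and power for that test.

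The sponsor may reply that the calculator returned 25. Its formula is not in the documents, and a reader might infer that it was misused. That is not supported and not needed: the ceiling binds every level-0.10 test under the stated inputs, whatever formula was used. One approximate log-rank formula does return 25 with 24 months of follow-up, but the plan states 6, and the exact ceiling with all 25 events is still 77.8%.

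Four stronger readings are tempting and should be resisted:

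- **That power is about 70% on any reading.** If both medians are scan-dated, the log-rank has 71–76% power, and an interval-censored test with a matching null has 79%. The plan does not state that reading, so the restated figure must carry its assumptions.
- **That type I error is inflated to 23–29%.** This holds only for an exact-time control. With a control scan-dated on a similar schedule, the same test is conservative, at 5–7%. The documents do not say which applies.
- **That an interval-censored test is therefore the right remedy.** Dating progression when recorded is a legitimate stated definition. If the control is scan-dated, an interval-censored test of an exact-time 4-month null has alpha of only 1.2–1.4% and power of 48–50%.
- **That later follow-up is of no use.** It recovers most of the shortfall, though it does not reach 80%.

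**Conclusion.** Wrong as written on power, and incomplete on analysis. On section 10.1's own inputs, 25 patients give at most about 71% power at one-sided 0.10, and 68–70% with the usual uncalibrated tests, against the stated 80%. The chance of missing a true 6-month median is about 3 in 10 instead of 2 in 10. These figures rest on exponential PFS, exact event times, uniform accrual at 2 per month, no loss and 6 months of follow-up, all as the plan states or implies.

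The missing test and success rule are established by the text alone. The gap is bounded: null, alternative, alpha and model are fixed, so a reader should not infer that the trial has no hypothesis. The effect of scan dating is conditional on how the control was dated, which the documents leave open. This should be fixed; it does not by itself call for more patients.

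**What to change.** 1. **Control first.** In section 10.1, state whether the 4-month control is a scan-dated or an exact-time median and, if scan-dated, on what schedule. Choose the test after that, because the log-rank on recorded dates is conservative in one case and anti-conservative in the other.
2. **Test and success rule.** In section 10.2, name one primary test that matches the sample-size calculation, for example a one-sample log-rank or an exponential likelihood test of median PFS = 4 months at one-sided 0.10, and state what result counts as success. Keep the Kaplan-Meier median with its Brookmeyer-Crowley interval as the descriptive summary, and give the interval's level.
3. **Power.** In section 10.1, restate power at N = 25 as about 68–71% for the named test, on the stated exponential, exact-time assumptions. If a later data cutoff is acceptable, the ceiling rises to about 75% at 12 months and 77% at 18 months.
4. **Alternative.** If only estimation is intended, say so in sections 3.2 and 10.1, remove the test wording, and justify 25 patients by the precision of the median.

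The cost is a few sentences and no extra patients. The downsides are a less favourable stated power and reliance on the exponential assumption. Restoring 80% would take 8 to 10 more patients, or 4 to 5 months of accrual at 2 per month; this fix does not require it.
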